5.6.2. Analysis of Secondary Efficacy Variables

Continuous Endpoints at visit 16

Change in the cumulative tolerated dose (log transformed) of peanut protein during a DBPCFC from baseline at visit 16 will be analyzed using analysis of covariance (ANCOVA) with treatment as the main effect, stratification variables and baseline tolerated cumulative amount of peanut protein DBPCFC (log transformed) as covariates. If subjects do not tolerate any dose level, they will be assigned a cumulative tolerated dose of 1 mg prior to converting to the log scale. The least-squares (LS) mean for each treatment group with its corresponding standard error (SE), the LS mean difference between treatment group and its corresponding SE and 95% CI, and the p-value corresponding to the between-treatment-group difference will be reported. In addition, change the

CONFIDENTIAL

Page 40 of 86

cumulative tolerated dose of peanut protein during a DBPCFC at visit 16 will be based on a non-parametric analysis using the van Elteren test.

Missing data for post up-dosing DBPCFC at visit 16 will be handled according to the reason for missingness as follows:

- If a subject misses the post up-dosing DBPCFC at visit 16 due to COVID-19, the missing data will be imputed by MI method for 10 times utilizing available post up-dosing DBPCFC data at visit 16. The MI will utilize regression method with treatment group, randomization stratification, and baseline tolerated cumulative amount of peanut protein DBPCFC (log transformed).
- If a subject does not have an available DBPCFC at visit 16 due to reasons not related to COVID-19, the baseline value at screening DBPCFC will be used to impute the missing post up-dosing DBPCFC data at visit 16.

Each of the complete datasets after the above steps will be analyzed by the ANCOVA. The SAS MIANALYZE procedure will then be used to generate valid statistical inferences by combining results.

Two sensitivity analyses will be performed as below to assess the robustness of results:

- Completed cases will be conducted regardless the rescue medication used.
- MI method: the missing data will be imputed by MI method utilizing available post updosing DBPCFC data at visit 16. The MI will utilize the same regression method as the above.

Continuous secondary efficacy endpoints that are measured repeatedly over time during the 28 to 40-week treatment period, will be analyzed using ANCOVA with treatment as the main effect, stratification variables and relevant baseline. For these endpoints, missing data will be imputed by multiple imputations (MI) methods 40 times to generate 40 complete data sets by using the Statistical Analysis System (SAS) procedure MI following the 2 steps below:

- Step 1: The monotone missing pattern is induced by Markov Chain Monte Carlo (MCMC) method in MI procedure using seed number 68367. The monotone missing pattern means that if a subject has missing value for a variable at a visit, then the values at all subsequent visits for the same variable are all missing for the subject.
- Step 2: The missing data at subsequent visits will be imputed using the regression method for the monotone pattern with seed number 81807 and adjustment for covariates including treatment groups, randomization stratification, and relevant baseline.

Each of the 40 complete datasets will be analyzed using an ANCOVA model with treatment group being the main factor, randomization stratification and baseline value as the covariate. The SAS MIANALYZE procedure will then be used to generate valid statistical inferences by combining results from the 40 analyses.

The least-squares (LS) mean for each treatment group with its corresponding standard error (SE), the LS mean difference between treatment group and its corresponding SE and 95% CI, and the p-value corresponding to the between-treatment-group difference will be reported.

Last observation carried forward (LOCF) method and worst observation carried forward (WOCF) will be employed as additional sensitivity analyses for continuous secondary efficacy endpoints that are measured repeatedly over time during the 28 to 40-week treatment period.

Percent change from baseline to visit 16 in peanut-specific IgE will be analyzed using rank-based ANCOVA with treatment as the main effect, stratification variables and baseline peanut-specific IgE level as covariates. The missing data will be imputed using MI method above. Last observation carried forward (LOCF) method will be employed as sensitivity analysis.

Binary Endpoints at visit 16

Proportion of subjects who reach 300 mg/day dose of AR101 by visit 16 will be analyzed using the Cochran-Mantel-Haenszel test adjusted by randomization stratification factors to assess the treatment difference in the proportion of subjects who reach the 300 mg/day dose of AR101 in the FAS. The proportion of subjects who reach the 300 mg/day dose of AR101 and its 95% confidence interval will be calculated for each treatment group with Clopper-Pearson confidence limits. Estimate of treatment difference, p-value, and the 2-sided 95% confidence interval using normal approximation will be provided.

Time-to-event Endpoint at visit 16

Time from randomization to the first time when subjects reach 300 mg/day dose of AR101 during the 28 to 40-week treatment period will be analyzed using the Cox proportional hazards model including treatment and randomization strata as factors. The hazards ratio, its 95% confidence interval and p-value will be reported. The Kaplan-Meier plots will be provided.

Continuous Endpoints at visit 22 and visit 25

Change in cumulative tolerated dose (log transformed) of peanut protein during a DBPCFC from baseline to visit 22 in subjects (continuously) treated with dupilumab plus AR101 vs placebo plus AR101, and change in cumulative tolerated dose (log transformed) of peanut protein during a DBPCFC from baseline to visit 22 in subjects (previously) treated with dupilumab plus AR101 (and re-randomized to placebo plus AR101) vs placebo plus AR101, will be assessed in a similar fashion as in visit 16 including missing data imputation and sensitivity analysis.

Percent change from baseline to visit 22 and visit 25 in peanut-specific IgE in subjects continuously treated with dupilumab + AR101 vs placebo + AR101 will be analyzed in a similar fashion as in visit 16.

Binary Endpoints at visit 22

Proportion of subjects (continuously) treated with dupilumab + AR101 vs placebo + AR10, and proportion of subjects (previously) treated with dupilumab + AR101 and re-randomized to placebo + AR101 vs placebo + AR101, who 'pass' a post-maintenance DBPCFC with 2044 mg cumulative peanut protein at visit 22 will be assessed the same way as for visit 16 including missing data imputation and sensitivity analysis.

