2.2. Statistical Hypothesis

The primary efficacy endpoint is the proportion of subjects who achieve a cumulative dose of 2044 mg peanut protein during a post up-dosing DBPCFC at visit 16. The comparison between the dupilumab + AR101 arm and the placebo + AR101 arm will be made.

Let p_D and p_P be the true proportions of subjects who achieve a cumulative dose of 2044 mg of peanut protein during a post up-dosing DBPCFC at visit 16 in the treatment arms of dupilumab + AR101 and placebo + AR101, respectively. The following hypothesis for the superiority testing will be tested at the 5% 2-sided significance level for the up-dosing phase:

H0: $p_D = p_P$, i.e., the proportion of subjects who achieve a cumulative dose of 2044 mg peanut

protein during a DBPCFC at visit 16 is the same between dupilumab + AR101 arm and the placebo + AR101 arm

against the alternative

Ha: $p_D \neq p_P$, i.e., the proportion of subjects who achieve a cumulative dose of 2044 mg peanut protein during a DBPCFC at visit 16 are different between the dupilumab + AR101 arm and the placebo + AR101 arm

CONFIDENTIAL

Page 13 of 86

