2.3. Sample Size and Power Considerations

It is assumed that the proportion of subjects who achieve a cumulative dose of 2044 mg of peanut protein during a post up-dosing DBPCFC at visit 16 in placebo plus AR101 arm will be 40%, based on an Aimmune presentation at the 2018 American Academy of Allergy, Asthma & Immunology–World Allergy Organization Joint Congress; with the proportion of subjects in dupilumab plus AR101 arm assumed to be 65%, which is considered to be clinical meaningful benefit by adding on dupilumab treatment. A sample size of approximately 156 subjects (104 in dupilumab plus AR101 and 52 in placebo plus AR101) will have 80% power to detect the treatment difference of 25% between placebo plus AR101 and dupilumab plus AR101 at the 2-sided 5% significance level (the minimum significant difference is approximately 17.8%). The sample size calculations were done by Fisher exact test using nQuery (7.0).

[figure not shown]
Approximately 122 subjects who undergo the post up-dosing DBPCFC at Week 28 (visit 16 with a window of -7/+30 days) as per protocol or discontinue from study prior to Week 28 (visit 16 with a window of -7/+30 days) will be included in the primary efficacy analysis. These subjects receive AR101 dose escalation per the original protocol's 24-week up-dosing schedule. The minimum significant difference with approximately 122 subjects is approximately 20.7% between placebo plus AR101 and dupilumab plus AR101 assuming placebo plus AR101 treatment effect is 40% at the 2-sided Fisher exact test with 5% significance level.

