3.1. The Full Analysis Set (FAS)

FAS includes all randomized subjects. Efficacy analyses will be based on the treatment allocated by the IWRS at randomization (as randomized).

The modified full analysis set (mFAS) includes all FAS subjects who undergo bi-weekly in-clinic up-dosing as described/specified in the protocol and undergo the post up-dosing DBPCFC at Visit 16/Week 28 (a window of -7/+30 days).

The mFAS will be considered as primary analysis set for all efficacy endpoints. The FAS will also be done for all efficacy endpoints as supportive analyses.

FAS-maintenance is a subset of FAS and includes subjects in the FAS who achieve 300 mg/day AR101 for at least 2 weeks in the up-dosing phase and re-randomized based on the treatment allocated by the IWRS at visit 16. The FAS-maintenance is the primary analysis set for efficacy analyses at visit 22.

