4.5. Efficacy Variable

4.5.1. **Primary Efficacy Variable (s)**

The primary endpoint in this study is:

• Proportion of subjects treated with dupilumab plus AR101 vs placebo plus AR101 who "pass" a post up-dosing DBPCFC with 2044 mg (cumulative) peanut protein at visit 16

Double-blind placebo-controlled food challenge (DBPCFC)

At visit 16, under intensive monitoring, all subjects who achieve 300 mg/day AR101 during the up-dosing phase for at least 2 weeks will undergo a post up-dosing DBPCFC up to 2044 mg (cumulative) peanut protein or placebo to assess desensitization. At visit 22, all subjects who maintain 300 mg/day AR101 will undergo a post maintenance DBPCFC up to 2044 (cumulative) peanut protein or placebo to assess desensitization. The subject's sensitivity to peanut allergen is defined as the dose at which the subject experiences allergic reactions. All symptoms and signs will be evaluated and rated based on a standardized oral food challenge scoring system (CoFAR). Up-dosing during the DBPCFC will be stopped when the principal investigator (or designee) finds symptoms and/or signs that indicate a definite objective (Grade 1 [mild]) allergic reaction (CoFAR grading system) has occurred based on clinically significant changes in reported symptoms, physical findings, or vital signs that the subject is experiencing to the challenge material. Vital signs will be assessed every 15 to 30 minutes. In addition, subjects will be considered to have dose-limiting reactions if they experience any mild subjective reactions requiring pharmacologic intervention and/or any moderate/severe reaction.

The DBPCFC will consist of 8 doses (peanut protein or placebo), given every 15 to 30 minutes: 1, 3, 10, 30, 100, 300, 600, 1000 mg, up to 2044 mg peanut protein (cumulative). Both peanut and oat protein will be concealed in a food that masks the taste. The food challenge will be performed on different days (1-day placebo [oat] protein, 1-day peanut protein, with order determined at random) at least 24 hours, but not more than 7 days apart, and not within 24 hours of a dose of study drug. Subjects will be considered to have passed the DBPCFC if they do not experience any objective Grade 1 (mild) reaction by CoFAR grading system. If the subject experiences reactions,

Regeneron Pharmaceuticals, Inc. Statistical Analysis Plan

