5.6.5. Subgroup Analysis

Subgroup analysis for the primary endpoint and the following secondary endpoints will be performed on mFAS and FAS-maintenance. Subgroups have been defined in Section 3.6.

- Change in cumulative tolerated dose (log transformed) of peanut protein during a DBPCFC from baseline to visit 16 in subjects treated with dupilumab plus AR101 vs placebo plus AR101
- Proportion of subjects treated with dupilumab plus AR101 vs placebo plus AR101 who reach the 300 mg/day dose of AR101 by visit 16
- Proportion of subjects (continuously) treated with dupilumab plus AR101 vs placebo plus AR101 who "pass" a post maintenance DBPCFC with 2044 mg (cumulative) peanut protein at visit 22
- Change in the cumulative tolerated dose (log transformed) of peanut protein during a DBPCFC from baseline to visit 22 in subjects (continuously) treated with dupilumab plus AR101 vs placebo plus AR101
- Proportion of subject (previously) treated with dupilumab plus AR101 (and re-randomized to placebo plus AR101) vs placebo plus AR101 who "pass" a post maintenance DBPCFC with 2044 mg (cumulative) peanut protein at visit 22
- Change in the cumulative tolerated dose (log transformed) of peanut protein during a DBPCFC from baseline to visit 22 in subjects (previously) treated with dupilumab plus AR101 (and re-randomized to placebo plus AR101) vs placebo plus AR101

The analysis method for the subgroup will be the same as the primary analysis described in Section 5.6.1 and Section 5.6.2. Interactions between the subgroups and treatment groups will be tested using the logistic regression model for the binary endpoints and using the ANCOVA model for the continuous endpoints. The model will include randomization strata, treatment group, subgroup, treatment by randomization strata interaction and treatment by subgroup interaction as factors. P-values for interaction term will be reported.

Forest plots of above efficacy endpoints across subgroups will be generated.

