10. APPENDIX

10.1. Summary of Statistical Analyses

Efficacy Analysis:

| Endpoints | Analysis Population | Primary Statistical Method | Supportive/Sensitivity Statistical Method | Subgroup Analysis | Other Analyses |
|---|------------------------|---|---|----------------------|----------------------|
| Primary Endpoint | | | · | | · |
| Proportion of subjects treated with dupilumab plus AR101 vs placebo plus AR101 who "pass" a post up- dosing DBPCFC with 2044 mg (cumulative) peanut protein at visit 16 | mFAS, FAS | Cochran-Mantel-Haenszel test/ MI for missing due to COVID-19, otherwise missing data as non-responder | Cochran-Mantel- Haenszel test with available visit 16 DBPCFC data | Yes | Bar chart |
| Secondary Endpoint | | | | | |
| Change in cumulative tolerated dose (log transformed) of peanut protein during a DBPCFC from baseline to visit 16 | mFAS, FAS | ANCOVA model/ MI for missing due to COVID-19, otherwise missing data imputed by BOCF method | ANCOVA model with available visit 16 DBPCFC data; MI method; van Elteren test with LOCF method/with available visit 16 DBPCFC data for change in cumulative tolerated dose | Yes | Bar chart |
| Proportion of subjects treated with dupilumab plus AR101 vs placebo plus AR101 who reach 300 mg/day dose of AR101 by visit 16 | mFAS, FAS | Cochran-Mantel-Haenszel test | No | Yes | Bar chart |
| Time from randomization to the first- time subjects reach the 300 mg/day dose of AR101 during up-dosing treatment phase (up to visit 16) | mFAS, FAS | Kaplan-Meier estimates; Cox regression model | No | No | Kaplan-Meier plot |

CONFIDENTIAL

Page 63 of 86

| Endpoints | Analysis Population | Primary Statistical Method | Supportive/Sensitivity Statistical Method | Subgroup Analysis | Other Analyses |
|---|------------------------|---|--|----------------------|-------------------|
| Proportion of subjects (continuously) treated with dupilumab plus AR101 vs placebo plus AR101 who 'pass' a DBPCFC with 2044 mg (cumulative) peanut protein at visit 22 | FAS- maintenance | Cochran-Mantel-Haenszel test/ MI for missing due to COVID-19, otherwise missing data as non-responder | Cochran-Mantel- Haenszel test with available visit 22 DBPCFC data | Yes | Bar chart |

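### The SAP conflicts on the analysis set for reaching 300 mg/day; on its own section 3.1 mFAS the proportion is 100% in both arms, and the time analysis covers only subjects who succeeded

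*SAP*

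**What the plan says.** **Analysis set for the proportion reaching 300 mg/day.**

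- SAP 5.6.2 applies the CMH test to subjects "who reach the 300 mg/day dose of AR101 in the FAS".
- SAP 3.1: "The mFAS will be considered as primary analysis set for all efficacy endpoints". SAP 5.6 repeats this and gives the FAS a supportive role.
- The SAP 10.1 table row reads "who reach 300 mg/day dose of AR101 by visit 16 | mFAS, FAS".
- SAP 5.6.5: "Subgroup analysis for the primary endpoint and the following secondary endpoints will be performed on mFAS and FAS-maintenance". The proportion reaching 300 mg/day is on the list that follows.

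**Analysis set for the time to 300 mg/day.** SAP 5.6.2 specifies a Cox model over the 28 to 40 week period and names no set, so the general rule in 3.1 and 5.6 applies. The 10.1 table again lists both sets. No subgroup analysis of this endpoint is planned.

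**Who is in the mFAS.** SAP 3.1 requires bi-weekly up-dosing as laid down in the protocol and a post up-dosing challenge at week 28 (window -7/+30 days). Protocol 11.3.1 has a wider set, which also includes subjects who leave the study before that visit. SAP 2.3 describes the primary analysis population in the same wider way. SAP 1.2.3, which lists departures from the protocol, does not mention a changed mFAS.

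**Who is challenged.** SAP 4.5.1 says that "all subjects who achieve 300 mg/day AR101 during the up-dosing phase for at least 2 weeks will undergo a post up-dosing DBPCFC". That gives one direction only. SAP 2.4 gives the other: the visit 16 challenge is conditional on at least two weeks at 300 mg/day, and subjects who fall short go to follow-up.

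**The concern.** These two secondary endpoints measure directly whether dupilumab lets more children complete up-dosing, and sooner. The protocol's study rationale names faster up-dosing as a question, and SAP 1.1 puts failure to complete up-dosing at up to 20%. SAP 1.2.3 removed the e-diary tolerability endpoints from the secondary list, so these two carry more of that question.

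A set defined by having been challenged is, under SAP 2.4, a set of subjects who reached the dose. Using it to ask how many reached the dose builds the answer into the denominator. Using it to ask how soon they reached it leaves out the failures and the slow achievers, who hold much of the information.

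**Working it through.** **1. The plan's own figure.** The documents give no power for the 300 mg/day endpoints. The sizing of the primary endpoint does reproduce: exact enumeration of the two-sided 5% Fisher test with 52 placebo and 104 dupilumab subjects, at 40% and 65%, gives power 0.811 against the stated 80%. The set sizes used below are therefore taken as stated.

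**2. Proportion on the SAP 3.1 mFAS.**

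- Membership requires a week 28 challenge (SAP 3.1).
- A challenge requires at least two weeks at 300 mg/day (SAP 2.4).
- So membership implies that the dose was reached, protocol deviations aside. The proportion is 100% in each arm and the difference is 0.

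The CMH variance in a stratum is n1 × n2 × m × (N − m) / [N² × (N − 1)], where m is the number reaching the dose. Treat 122 subjects as one stratum, split 41/81 at about 1:2, with m = N = 122. Then 41 × 81 × 122 × 0 / (122² × 121) = 0. The same holds in every stratum, so there is no test statistic. The logistic interaction model in SAP 5.6.5 would have an outcome of 1 for every subject and could not be fitted.

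**3. Proportion on the FAS.** Take 80% on placebo (an assumption, from the figure of up to 20% failing) and 90% on dupilumab (assumed). The difference is 90 − 80 = 10 points. Fisher power at 52/104 for assumed rates:

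| Placebo | Dupilumab | Power |
|---|---|---|
| 80% | 90% | 0.35 |
| 80% | 95% | 0.78 |
| 70% | 90% | 0.84 |

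The FAS analysis is informative, though not strong for a modest difference.

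**4. Proportion on the wider mFAS (protocol 11.3.1, SAP 2.3).** About 156 − 122 = 34 subjects are excluded. Assume a split of 11 placebo and 23 dupilumab, with all 34 reaching the dose later, and FAS rates of 80% and 90%.

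- Placebo: (52 × 0.80 − 11) / (52 − 11) = 30.6 / 41 = 74.6%.
- Dupilumab: (104 × 0.90 − 23) / (104 − 23) = 70.6 / 81 = 87.2%.

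The result is not degenerate, but the difference is about 12.5 points where the FAS gives 10. The exclusion alone has moved it.

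**5. Time to 300 mg/day on the SAP 3.1 mFAS.** Protocol Table 2 first reaches 300 mg at week 24. The week 28 target is day 197, so the window closes on day 197 + 30 = 227. With two weeks at dose beforehand, 300 mg must be reached by day 227 − 14 = 213, and (213 − 1) / 7 gives about week 30. SAP 5.6.2 defines the endpoint over 28 to 40 weeks. Later achievers and subjects who never reach the dose are absent, and everyone left has an event.

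The hazard ratio can still differ from 1. An illustrative simulation used 41 and 81 subjects, all with events between about weeks 24 and 30, and an assumed delay probability per two-week step of 0.35 on placebo and 0.15 on dupilumab. It gave a median hazard ratio of about 2.1 (2.5th to 97.5th percentile 1.46 to 3.29). On a strict reading of the up-dosing condition in SAP 3.1, the times would be nearly constant.

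**The case against.** **The endpoint-specific text already says FAS.** SAP 5.6.2 can be read as overriding the general rule, and 10.1 plans the FAS run anyway. This stands to the extent that the fault is a conflict and not a settled choice of the mFAS. It does not resolve the conflict: 3.1 and 5.6 cover all efficacy endpoints without exception, 5.6.5 provides no FAS subgroup run for the proportion, and 5.6.2 names no set for the Cox model.

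**The 100% result rests on one definition.** SAP 2.3 and protocol 11.3.1 keep early discontinuers. The missing-challenge rules in SAP 5.6.1 would also have no one to act on under 3.1, which suggests that the wider set was intended. This stands. The degenerate result follows from the SAP 3.1 wording only.

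**The extension visits also served COVID-19 restrictions.** True, so removing those subjects is not purely selection on tolerability. But protocol 6.1 also allows the extension for dose reductions and re-escalation, which treatment may affect.

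**The consequences are limited.** Neither endpoint is in the testing hierarchy of SAP 5.6.3, and a table showing 100% in both arms would be noticed. Both points are fair and keep this below a critical finding. A time analysis restricted to successes would be harder to notice.

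**Conclusion.** The SAP gives conflicting analysis sets for the proportion reaching 300 mg/day. On the set its general rule makes primary, as defined in 3.1, that proportion is 100% in both arms, protocol deviations aside, and neither the CMH test nor the subgroup interaction model is defined. With assumed true rates of 80% and 90%, a 10-point FAS difference would appear as 0.

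A reader might infer that both endpoints are fixed by construction. The documents do not support that for the time endpoint: its hazard ratio is free, but the comparison is conditioned on success by about week 30. Nor do they support saying that every version of the mFAS is degenerate. Under protocol 11.3.1 and SAP 2.3 the proportion stays below 100% whenever a subject discontinues without reaching the dose, although exclusion after randomization can still shift the difference.

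The logic rests on the documents alone. The attainment rates, the 11/23 split and the delay probabilities are illustrative assumptions. This should be corrected before database lock. It does not affect the primary endpoint's alpha.

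**What to change.** - Name the FAS as the primary set for the proportion reaching 300 mg/day, for the time to 300 mg/day, and for the subgroup analysis of the proportion. Write this as an explicit exception in SAP 3.1 and 5.6, and carry it into 5.6.2 (including the Cox model), 5.6.5 and the two rows of the 10.1 table.
- State one mFAS definition in the SAP, consistent with protocol 11.3.1.
- In the time analysis, censor subjects who never reach 300 mg/day and state the date at which they are censored.

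The cost is SAP wording plus one FAS subgroup run for the proportion. The main FAS analyses are already planned and no new data are needed.

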2. INVESTIGATION PLAN

2.1. Study Design and Randomization

This is a Phase 2, multicenter, randomized, double-blind, parallel-group, 2-arm study in subjects aged 6 to 17 years inclusive who are allergic to peanut. The study consists of a screening period of up to 16 weeks, a 28 to 40-week double-blind treatment period, a 24-week maintenance phase, and a 12-week post-treatment follow-up period. In protocol amendment 3 to accommodate COVID-19 restrictions, double-blind treatment period was extended from 28 weeks to up to 40 weeks. Subjects who attend optional visits between week 28 and week 40 will have increased duration of exposure to AR101 and dupilumab.

Approximately 156 subjects will be randomized at baseline in a 2:1 ratio into one of 2 treatment arms (n=104 to dupilumab and 52 to placebo, in combination with up-dosing of AR101) according to a central randomization scheme provided by an IWRS. Randomization will be stratified by screening peanut-specific IgE level ($\leq 100 \text{ kUA/L}$ or $\geq 100 \text{ kUA/L}$) and body weight ($\leq 30 \text{ kg}, \geq 30 \text{ kg}$ and $\leq 60 \text{ kg}$, or $\geq 60 \text{ kg}$) at randomization. A minimum of 15 subjects for each weight group will be enrolled.

At visit 16 (or at the early termination visit for those who discontinue from study prior to visit 16), subjects previously in the dupilumab plus AR101 arm will be re-randomized in a 1:1 ratio into one of 2 treatment arms (dupilumab versus placebo, in combination with AR101), according to a central randomization scheme provided by IWRS. Randomization will be stratified by whether subjects achieve 300 mg/day AR101 for at least 2 weeks by visit 16 (Yes or No).

Subjects previously in the placebo plus AR101 arm will continue their treatment of placebo plus AR101 in the maintenance phase if they achieve 300 mg/day AR101 for at least 2 weeks at visit 16.

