5.6.1. Analysis of Primary Efficacy Variable

This primary endpoint will be analyzed using the Cochran-Mantel-Haenszel (CMH) test adjusted by randomization stratification factors (screening peanut-specific IgE level [\leq 100 kUA/L or >100 kUA/L] and baseline body weight [<30 kg, \geq 30 kg and <60 kg, or \geq 60 kg]) to assess the treatment difference in the proportion of responders (i.e., those who "pass" a post up-dosing DBPCFC with 2044 mg [cumulative] peanut protein at visit 16 [Week 28 with a visit window of -7/+30 days]) in the mFAS.- Estimate of treatment difference, p-value, and the 2-sided 95% confidence interval using CMH test will be provided. The number and percent of subjects at each dose level for highest tolerated peanut protein dose at post up-dosing DBPCFC will also be summarized.

The primary estimand of interest for the primary endpoint is described as follows, based on intercurrent event(s) strategy and missing data handling methods:

- The treatment policy strategy will be implemented for the intercurrent event of the treatment discontinuation. The data collected after the patient discontinued treatment will be included in the analysis.
- Missing data for post up-dosing DBPCFC at visit 16 will be handled according to the reason for missingness as follows:
 - If a subject misses the post up-dosing DBPCFC at visit 16 due to COVID-19, the missing data will be imputed by multiple imputation (MI) method for 10 times utilizing available post up-dosing DBPCFC data at visit 16. The MI will utilize logistic regression method with treatment group and randomization stratification.
 - If a subject does not have available DBPCFC data with peanut protein at visit 16 due to reasons not related to COVID-19, this subject will be considered as a nonresponder at visit 16.

Each of complete datasets after the above steps will be analyzed by the CMH test. The SAS MIANALYZE procedure will then be used to generate valid statistical inferences by combining results using Rubin's formula (Rubin, 1987).

Sensitivity analyses will include an analysis of the subset of subjects with available visit 16 DBPCFC data with peanut protein.

The supportive analyses based on FAS and PPS will be performed using primary analysis method.

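### For the proportion reaching 300 mg/day, the normal-approximation interval for the treatment difference is unreliable in a weight group near its 15-subject floor and should be a score-type interval on a reconciled population

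*SAP*

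**What the plan says.** SAP 5.6.2 (Binary Endpoints at visit 16) analyses this endpoint with a stratified Cochran-Mantel-Haenszel (CMH) test. Each arm's own proportion gets an exact interval: it "will be calculated for each treatment group with Clopper-Pearson confidence limits". The difference between arms does not: "Estimate of treatment difference, p-value, and the 2-sided 95% confidence interval using normal approximation will be provided". The form of variance is not named.

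SAP 5.6.5 lists this endpoint among those analysed by subgroup and adds: "The analysis method for the subgroup will be the same as the primary analysis described in Section 5.6.1 and Section 5.6.2". It then says: "Forest plots of above efficacy endpoints across subgroups will be generated". Weight group is one of the subgroups in SAP 3.6. On its size, SAP 2.1 says: "A minimum of 15 subjects for each weight group will be enrolled". No fallback is given for sparse groups or for proportions at 100%.

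The other forest-plot endpoints are treated differently. For passing the food challenge at visit 16, SAP 5.6.1 says "the 2-sided 95% confidence interval using CMH test will be provided", and visit 22 follows the same method. The tolerated-dose endpoints use ANCOVA.

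The population for this endpoint is stated three ways: FAS in SAP 5.6.2, mFAS and FAS in SAP Appendix 10.1, and for subgroups in SAP 5.6.5: "Subgroup analysis for the primary endpoint and the following secondary endpoints will be performed on mFAS and FAS-maintenance".

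**The concern.** The standard error of a simple difference in proportions shrinks as both proportions approach 1, and it is exactly zero when nobody fails in either arm. This endpoint is expected to be high, and some rows of the forest plot may be small. A row built on 15 children could then show a tight interval, or a difference of 0 with no error bar at all. Readers of a forest plot rely on interval widths to discount small groups, so the display would mislead most where the data are thinnest. The SAP already uses an exact method within each arm, so nothing in the plan explains the weaker choice for the difference.

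**Working it through.** **Inputs.**
- Arm sizes: "Approximately 156 subjects will be randomized at baseline in a 2:1 ratio into one of 2 treatment arms" (SAP 2.1), so 104:52 overall. A third of 156 is 52 subjects (about 35:17), a half is 78 (52:26), and the floor of 15 is 10:5.
- Success rate without dupilumab: protocol Section 1 and SAP 1.1 say up to 20% cannot complete up-dosing, giving about 80%. Protocol 3.2.1 cites a peanut cohort in which 86% tolerated up-dosing.
- Success rate with dupilumab: the documents give none. Rates up to 95% are an assumption.

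**The plan's own figures.** The documents state no coverage figure for this interval. Their 80% Fisher power for 65% vs 40% at 104:52 reproduces by enumeration as 81.1%, which confirms the arm sizes.

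**Method.** Let a and b be the observed proportions among n1 and n2 subjects. The simple normal-approximation (Wald) interval is a − b ± 1.96 √[a(1−a)/n1 + b(1−b)/n2]. Coverage is the sum of binomial probabilities over all outcomes whose interval contains the true difference. The interval has zero width when each arm is at 0% or 100%.

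**Results at 10:5** (true rates, dupilumab/placebo):

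| True rates | Wald coverage | Zero width | Newcombe coverage |
|---|---|---|---|
| 85/80 | 77.0% | 6.5% | 98.1% |
| 90/85 | 71.8% | 15.5% | 98.9% |
| 90/80 | 64.8% | 11.4% | 97.3% |
| 95/80 | 63.5% | 19.6% | 99.4% |
| 95/90 | 59.0% | 35.4% | 99.5% |
| 95/85 | 53.9% | 26.6% | 98.3% |
| 80/80 | 86.9% | 3.5% | 95.2% |
| 85/85 | 90.5% | 8.7% | 95.7% |
| 90/90 | 95.2% | 20.6% | 96.8% |

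One cell by hand: at 95/85 the zero-width chance is 0.95^10 × 0.85^5 = 0.599 × 0.444 = 0.266.

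The equal-rate rows need care. At 90/90, 20.6 of the 95.2 points come from zero-width intervals that count as correct only because the true difference happens to be 0. At 95/95 (not tabulated), coverage is 99.0%, with zero width in 46.3% of trials.

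**Wald coverage in larger groups**, same nine pairs:
- 104:52: 92.6-94.4% (92.1% at 95/95).
- 52:26: about 92-93.5%.
- 35:17: about 83-93%. Eight of the nine pairs lie between 90.8% and 92.8%; the low value is 82.6% at 95/90.

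**Does a stratified form rescue it?** A Mantel-Haenszel risk difference with Sato variance was simulated (200,000 runs) with the 15 subjects split into two strata. It gave 76.7%, 64.8%, 53.8% and 59.1% at 85/80, 90/80, 95/85 and 95/90. The result barely changes.

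**What the alternative shows.** Suppose 10/10 and 5/5 succeed. The Wald interval is 0 to 0. The Wilson lower limits are 10/(10 + 3.84) = 0.722 and 5/(5 + 3.84) = 0.566. The Newcombe interval therefore runs from −(1 − 0.722) = −0.278 to 1 − 0.566 = 0.434.

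**Population.** SAP 3.1 limits the mFAS to subjects who undergo the visit 16 challenge. SAP 2.4 gives that challenge to subjects who have been at 300 mg/day for at least 2 weeks. Read together, nearly all mFAS subjects in both arms have reached the endpoint, and a Wald interval collapses toward zero width at any sample size. Protocol 11.3.1 also counts subjects who discontinued before week 28, and so does SAP 2.3 in describing the 122.

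**The case against.** The strongest reply is that the problem is narrow, and much of that stands.

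A reader might infer that all the subgroup forest plots are affected. They are not: of the primary and six secondary endpoints listed in SAP 5.6.5, only this one has a stated normal-approximation interval.

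A reader might also take 54-77% as the general performance at high rates. It needs a group at 10:5 and truly unequal arms. Fifteen is a recruitment floor, not an expected size; equal thirds would give 52 per weight group. Age, sex and IgE are two-level subgroups, and the asthma and atopic dermatitis subgroups are reserved for the primary and key secondary endpoints. On the other side, the floor applies to enrolment while subgroups run on the mFAS. At 122 of 156, a group of 15 would shrink to about 12 (15 × 122/156 = 11.7).

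It is tempting to add that the interval will contradict the CMH p-value. That depends on reading the interval as unstratified, which the SAP does not say, and on stratum rates that the documents do not give.

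Finally, SAP 5.6.3 keeps this endpoint outside the controlled hierarchy, subgroup claims have their own interaction test, and the overall analysis reports exact limits for each arm beside the difference. These points limit the consequence. They do not make the stated interval sound in a small group.

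**Conclusion.** The point holds for one endpoint. Overall, the interval is slightly too narrow and the effect is minor. In subgroup rows the error grows as groups shrink and becomes serious for a weight group near its floor, where coverage can fall to between one half and three quarters and the interval can vanish. These figures assume true rates of 80-95%, of which only about 80-86% on immunotherapy alone has support in the documents. The low figures at 10:5 also require a real difference of 5-15 points between arms.

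The confirmatory tests are untouched. The change is worth making because it is cheap and the replacement performs better throughout the small-group cases checked. It is incomplete alone: if the SAP's mFAS wording stands, the comparison is close to 100% against 100%, and no interval method makes that informative.

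**What to change.** In SAP 5.6.2, replace the normal approximation for the difference with a stratified score-type interval (stratified Newcombe or Miettinen-Nurminen), using the same strata as the CMH test. In SAP 5.6.5, state that subgroup rows for this endpoint use a Newcombe or Miettinen-Nurminen interval, unstratified where strata are too sparse, and define sparse in advance.

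In the same revision, name one primary population for this endpoint consistently in SAP 5.6.2, 5.6.5 and Appendix 10.1. Also reconcile the mFAS definition in SAP 3.1 with protocol 11.3.1 and SAP 2.3, so that subjects who fail to reach 300 mg/day are not removed from the denominator by definition.

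The interval change costs a line or two of wording and a different standard software option, with no new data. Intervals become somewhat wider, and in sparse subgroups an unstratified interval may not agree exactly with the CMH p-value; a footnote to the forest plot should say so. The population change needs a decision before database lock.
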